5.4. Study Drug Administration

Study drug will be administered subcutaneously to all patients in the clinic by designated and trained site staff from Baseline through the Week 8 visit and at all other scheduled clinic visits. Following the Week 8 visit, patients will be allowed to administer study drug at home. Sufficient study drug should be dispensed to cover at home administrations through next study visit.

5.4.1. Instructions for Administration in the Clinic

Syringes should be at room temperature prior to injection (refer to the applicable Instructions for Use provided by the Sponsor).

5.4.2. Instructions for Administration at Home

Patients or caregivers will be instructed to self-administer study drug at the Week 8 visit.

Study site staff will instruct the patient or their caregiver on the proper injection technique and the patient or their caregiver will demonstrate for site staff proper injection technique prior to beginning at-home administration. An instruction card with details of the injection procedures will be provided to the patient/caregiver to take home.

Patients or caregivers who are not capable of administering study drug at home may continue to receive study drug injections in the clinic.

5.5. Study Drug Accountability

The Investigator must keep an accurate record of the number of cartons received, the study drug dispensed/used, and those returned to the Sponsor or designee. The Sponsor or designee will provide forms to facilitate inventory control. All study-drug accountability forms and treatment logs must be retained in the Investigator's permanent study file, and these records must be available for inspection at any time by the Sponsor, its designees, or by regulatory agencies.

The study monitor will perform drug accountability for all study drug at the site, and will assist in returning all used, unused, and expired study drug, to the Sponsor/designees, or destroy it according to the study site's standard operating procedure, if accepted by the Sponsor.

6. CONCOMITANT MEDICATIONS AND PROCEDURES

All medications (including over-the-counter drugs, vitamins, and antacids) and over-the-counter emollient(s) taken/used at screening and throughout the study must be recorded. Patients should be instructed to consult with the Investigator prior to initiating any new medication (either self-administered non-prescription drugs or prescription therapy prescribed by another physician) while participating in the study. The Investigator is expected to examine the acceptability of all concomitant medications, topical preparations, and dietary supplements taken by patients participating in the trial.

- Medication entries should be specific to product name (if a combination drug product) and spelled correctly.
- The brand and specific product name for any over-the-counter emollient(s) should be noted and spelled correctly.
- Information on the dose, unit, frequency, route of administration, start date, discontinuation date, indication, and reason for use will be recorded.
- The use of any concomitant medication must relate to an AE listed on the AE electronic case report form (eCRF) or the patient's medical history unless it is a supplement or used as preventative care.

6.1. Permitted and Prohibited Treatments and Procedures

The use of concomitant medications for other medical conditions (e.g., hypertension, diabetes, acute infections) is permitted during this study. Inhaled corticosteroids and bronchodilators to control asthma are permitted.

The introduction of medications or therapies for other medical conditions known to affect AD (e.g., systemic corticosteroids, mycophenolate-mofetil, IFN- γ , Janus kinase inhibitors, TCI, cyclosporine, azathioprine, methotrexate, phototherapy, or photochemotherapy, crisaborole) are not permitted during the study. If systemic corticosteroids are required for treatment of AE or other medical conditions (e.g. worsening of existing condition such as asthma exacerbation), it can be used for short periods of time as per medical judgement. Patients requiring long-term systemic corticosteroids for treatment of AE or other medical conditions must be discontinued from the study.

Acute infections can be treated with systemic antibiotics, the use of which must be recorded in the eCRF. However, chronic treatment with systemic antibiotics is not permitted.

Additional drugs are to be avoided during the study unless required to treat an AE or for the treatment of an ongoing medical problem. If the need for concomitant medication arises, the investigator should base decisions on the patient and clinical factors. Any additional medication (including the limited use of therapeutic agents which, if used under treatment regimens other than for treatment an AE or for appropriate medical management, might be considered therapies) whether prescription or over-the-counter, used at baseline and/or during the course of the study, must be documented with the start and stop dates.

The use of a tanning booth/parlor is not permitted during the trial.

Planned or anticipated major medical procedures or surgeries should be avoided during the trial.

All concomitant medications and procedures must be recorded in the eCRF.

6.2. Moisturizers

Non-medicated moisturizers are to be used during the study. Patients may continue her/his current over-the-counter moisturizer regimen, if approved by the Investigator. Non-medicated moisturizer should be used daily throughout the study.

6.3. Treatments for AD

TCS, TCIs and PDE4 inhibitors may be used as needed to treat disease flares during the trial. Patients who may require short-term systemic treatment for symptoms of AD will be assessed on a case-by-case basis and must be discussed with the Medical Monitor prior to initiating treatment.

Cannabinoid treatments for AD are prohibited.

Patients requiring long-term systemic treatment for symptoms of AD (e.g., non-responders) must be discontinued from the study.

Medications used for AD must be recorded in the eCRF.

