1.3.1.2. Summary of Study GS29735 (ARBAN)

Study Design

ARBAN was a Phase 2, randomized, open-label study designed to evaluate the safety and efficacy of lebrikizumab monotherapy in adult patients (18–75 years of age) with persistent moderate to severe AD, who were inadequately controlled by TCS. A total of 55 patients were randomized to treatment: 28 to lebrikizumab 125 mg Q4W and 27 to TCS.

Efficacy Results

- EASI-50 was achieved by 53.6% and 51.9% of patients in the lebrikizumab and TCS groups, respectively, with a treatment difference of 1.7%. EASI-75 was achieved by 39.3% and 37.0% of patients in the 2 groups, respectively, with a treatment difference of 2.3%.
- Investigator Global Assessment (IGA) scores of 0 or 1 were observed for 7.1% of patients in the lebrikizumab group and 25.9% of patients in the TCS group, giving a treatment difference of –18.8% (95% CI: –37.9%, 0.3%).
- The percent of patients achieving SCORAD-50 or SCORAD-75 showed treatment differences of –19.3% and –7.5%, respectively.

Safety Results

- AEs were reported for a higher proportion of patients in the lebrikizumab group compared with the TCS group (64.3% vs. 37.0%); a higher proportion of patients in the lebrikizumab group, compared with the TCS group, had an AE in the SOC of infections and infestations (42.9% vs. 25.9%). Upper respiratory tract infections were more common in the lebrikizumab group (14.3% vs. 3.7%).
- The overall incidence of skin infection (in the SOC of infections and infestations) was 17.9% in the lebrikizumab group and 7.4% in the placebo/TCS group.
- No serious AEs (SAEs), deaths, anaphylaxis, malignancy, protocol-defined parasitic or targeted intracellular infections of interest, herpes viral infections or zoster, or eosinophilia-associated AEs were reported.

Conclusions

Lebrikizumab was well tolerated at the dose of 125 mg Q4W; the safety profile was generally consistent with previous experience with lebrikizumab in previous trials.

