4.1. Inclusion Criteria

Patients must meet all the following criteria to be eligible for this study:

1. Male or female adolescent (≥ 12 years to < 18 years and weighing ≥ 40 kg).
2. Chronic AD (according to American Academy of Dermatology Consensus Criteria) that has been present for ≥ 1 year before the screening visit (see [Appendix 2](#)).
3. Eczema Area and Severity Index (EASI) score ≥ 16 at the baseline visit.
4. Investigator Global Assessment (IGA) score ≥ 3 (scale of 0 to 4) at the baseline visit.
5. $\geq 10\%$ body surface area (BSA) of AD involvement at the baseline visit.
6. History of inadequate response to treatment with topical medications; or determination that topical treatments are otherwise medically inadvisable.
7. Apply a stable dose of non-medicated, non-prescription moisturizer at least twice daily for ≥ 7 days prior to the baseline visit.
8. Willing and able to comply with all clinic visits and study-related procedures and questionnaires.
9. For women of childbearing potential: agree to remain abstinent (refrain from heterosexual intercourse) or use a highly effective contraceptive method during the treatment period and for at least 18 weeks after the last dose of lebrikizumab.

NOTE: A woman of childbearing potential is defined as a postmenarcheal female, who has not reached a postmenopausal state (≥ 12 continuous months of amenorrhea with no identified cause other than menopause) and has not undergone surgical sterilization (removal of ovaries and/or uterus).

NOTE: The following are highly effective contraceptive methods: combined (estrogen and progestogen containing) hormonal contraception (oral, intravaginal, transdermal) associated with inhibition of ovulation, progestogen-only hormonal contraception (oral, injectable, implantable) associated with inhibition of ovulation, intrauterine device,

intrauterine hormone-releasing system, bilateral tubal occlusion, bilateral tubal ligation, vasectomized partner, or sexual abstinence. The reliability of sexual abstinence should be evaluated in relation to the duration of the clinical trial and the preferred and usual lifestyle of the patient. Periodic abstinence (e.g., calendar, ovulation, symptothermal, or postovulation methods) and withdrawal are not acceptable methods of contraception.

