4.2. Exclusion Criteria

Patients meeting any of the criteria below will be excluded from this study:

1. Participation in a prior lebrikizumab clinical study.
2. History of anaphylaxis as defined by the Sampson criteria ([Sampson, 2006](#)).
3. Treatment with topical corticosteroids, calcineurin inhibitors or phosphodiesterase-4 inhibitors (e.g., crisaborole) within 1 week prior to the baseline visit.
4. Treatment with any of the following agents within 4 weeks prior to the baseline visit:
 - a. Immunosuppressive/immunomodulating drugs (e.g., systemic corticosteroids, cyclosporine, mycophenolate-mofetil, IFN- γ , Janus kinase inhibitors, azathioprine, methotrexate, etc.)
 - b. Phototherapy and photochemotherapy (PUVA) for AD.
5. Treatment with the following prior to the baseline visit:
 - a. An investigational drug within 8 weeks or within 5 half-lives (if known), whichever is longer.
 - b. Dupilumab within 8 weeks.
 - c. B cell-depleting biologics, including to rituximab, within 6 months.
 - d. Other biologics within 5 half-lives (if known) or 16 weeks, whichever is longer.
6. Use of medicated prescription moisturizers within 7 days of the baseline visit.
7. Regular use (more than 2 visits per week) of a tanning booth/parlor within 4 weeks of the screening visit.
8. Treatment with a live (attenuated) vaccine within 12 weeks of the baseline visit or planned during the study.
9. Uncontrolled chronic disease that might require bursts of oral corticosteroids, e.g., co-morbid severe uncontrolled asthma (history of ≥ 2 asthma exacerbations within the last 12 months requiring systemic [oral and/or parenteral] corticosteroid treatment or hospitalization for > 24 hours).
10. Active chronic or acute infection requiring treatment with systemic antibiotics, antivirals, antiparasitics, antiprotozoals, or antifungals within 2 weeks before the baseline visit, or

superficial skin infections within 1 week before the baseline visit.

NOTE: patients may be rescreened after infection resolves.

11. Evidence of active acute or chronic hepatitis (as defined by the Department of Health & Human Services Centers for Disease Control and Prevention) or known liver cirrhosis.
12. Diagnosed active endoparasitic infections or at high risk of these infections.

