8.6.2. Study Drug Discontinuation

Study drug must be discontinued for patients who experience the following:

- Inter-current illness that would, in the judgment of the Investigator, affect assessments of clinical status to a significant degree
- Treatment-related AEs that are clinically significant, deemed persistent, in the judgment of the Investigator
- Unacceptable toxicity
- Pregnancy
- Use of rescue medication as outlined in Section 6.3

Patients who discontinue study drug permanently during study participation must be scheduled for an Early Termination visit (Section 7.18).

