7.1.2. General Considerations for Analyses

Data will be summarized using descriptive statistics. No inferential testing will be performed. Categorical variables will be tabulated with frequencies and percentages. Continuous variables will be tabulated with mean, median, standard deviation, and range (minimum and maximum).

Baseline will be defined as the last available value before the first injection for efficacy and health outcome analyses. In most cases, this will be the measure recorded at the baseline visit (Day 1). If the patient does not take any injection, the last available value on or prior to treatment assignment date will be used. Change from baseline will be calculated as the visit value of interest minus the baseline value.

For the safety analyses, the following baselines will be used. For safety analyses using a baseline period, the baseline period is defined as the time from the screening visit to the date/time of the first injection

- TEAEs: baseline will be all results recorded during the baseline period.
- Treatment-emergent abnormal laboratory and vital signs results: baseline will be all results recorded during the baseline period.
- Change from baseline to last postbaseline observation or to each scheduled postbaseline visit for laboratory and vital signs results: baseline will be the last scheduled nonmissing assessment recorded during the baseline period.

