7.3.1. As Observed Analysis

The “as observed” strategy is used in so-called “observed cases” or “completers” analysis ubiquitous in the literature but is not one of the recommended strategies in the ICH E9(R1). For this analysis, only data from completers at the visit are relevant. Therefore, this estimand is conditional and targets the effect of treatment conditional on completion of treatment through the time point of interest. Because the estimand is defined for a subpopulation conditional on an intercurrent event, it is not causal. Summaries based on observed data at each postbaseline visit will be provided. All efficacy and health outcome endpoints will be summarized using an “as observed” analysis.

A large, stylized red watermark consisting of the letters 'CCI' is centered on a solid black rectangular background. The letters are bold and serifed.

The image shows the letters 'CCI' in a large, bold, red serif font. The letters are set against a solid black rectangular background that occupies the upper half of the page.

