7.9. Prior and Concomitant Therapy

Medications will be classified into anatomical therapeutic chemical drug classes using the latest version of the WHO drug dictionary. Medication start and stop dates will be compared to the date of first dose of treatment to be classified as prior or concomitant.

Prior medications are those medications that start and stop prior to the date of first dose of study treatment. *Concomitant medications* are those medications that start before, on, or after the first day of study treatment and continue into the treatment period.

Prior medication and concomitant medication will be summarized by drug class and PT for the safety population.

Rescue medications used during the study treatment period will be presented for the safety population based on the information collected on the *Atopic Dermatitis Treatments* eCRF page. This will include: (1) topical therapy, (2) systemic therapy (e.g., systemic corticosteroids, phototherapy, cyclosporin, etc.). More information on the definition of rescue medications can be found in [Appendix 1](#).

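### IGA (0,1) and EASI-75 are measured from an off-topical baseline but may be reached with as-needed topicals, so they describe lebrikizumab plus topicals, not lebrikizumab alone

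*Protocol*

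**What the plan says.** **Baseline.** Exclusion criterion 3 (Protocol 4.2) rules out "Treatment with topical corticosteroids, calcineurin inhibitors or phosphodiesterase-4 inhibitors (e.g., crisaborole) within 1 week prior to the baseline visit". Severity for entry is set at that same visit, for example "Eczema Area and Severity Index (EASI) score ≥ 16 at the baseline visit" (Protocol 4.1). SAP 7.1.2 makes it the reference for change and response: "Baseline will be defined as the last available value before the first injection for efficacy and health outcome analyses".

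**After baseline.** Protocol 6.3: "TCS, TCIs and PDE4 inhibitors may be used as needed to treat disease flares during the trial". It gives no ceiling on potency, quantity or duration and no topical-free interval before the IGA/EASI/BSA assessments at Weeks 4, 8, 16, 32 and 52 (Protocol Appendix 1). Protocol 6.1 also allows short courses of systemic corticosteroids for an adverse event or another condition.

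**Analysis.** SAP 7.3 names rescue treatment as an example of an intercurrent event, and SAP Appendix 1 classes TCS, TCIs and crisaborole as rescue. SAP 7.3.1 applies to all efficacy endpoints: "Summaries based on observed data at each postbaseline visit will be provided". It conditions on completing treatment to the visit and has no rule for rescue. The IGA and EASI definitions in Table KGAE.7.3 carry no rescue condition. LOCF and MCMC-MI summaries are also planned (SAP 7.10), but the sections that define them are blacked out.

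**Reporting of rescue.** SAP 7.9: "Rescue medications used during the study treatment period will be presented for the safety population", drawn from the Atopic Dermatitis Treatments eCRF page. The efficacy subgroups named in SAP 7.14.1 are region and weight.

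**Stopping rule.** Protocol 8.6.2 lists "Use of rescue medication as outlined in Section 6.3" among the events for which study drug must be discontinued.

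**The concern.** Change from baseline compares a visit without topicals with visits that may be on them. In a randomised trial a control arm under the same rules would carry the topical contribution too. Here SAP 6.3 assigns every patient to lebrikizumab, so nothing removes it. Under Protocol 6.3 as written, a patient who reaches IGA 0 or 1 with the help of a potent TCS counts as a responder in the as-observed tables.

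Efficacy is half of the stated objective. If the percentages are quoted without qualification, readers will take them as the effect of the antibody. The protocol's own summary of an earlier adult study (GS29735, Protocol 1.3.1.2) gives reason for care: in patients inadequately controlled by TCS, the arm given TCS without lebrikizumab reached these same endpoints in appreciable numbers.

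**Working it through.** **1. Reproduce a figure in the documents.** The sample-size sections are blacked out, so there is no power or effect figure to check. The nearest checkable figure is the IGA 0/1 difference in the earlier adult study.
- Inputs: 7.1% of 28 is 2 patients (lebrikizumab 125 mg Q4W); 25.9% of 27 is 7 patients (TCS).
- Formula: d ± 1.96 × √[p1(1−p1)/n1 + p2(1−p2)/n2].
- Result: 2/28 − 7/27 = −18.8%, 95% CI −37.9% to 0.3%. This matches the protocol exactly.

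**2. What TCS without lebrikizumab did in that study.** The protocol reports "EASI-75 was achieved by 39.3% and 37.0% of patients in the 2 groups, respectively", the second group being TCS. With exact (Clopper-Pearson) intervals:

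| Endpoint, TCS arm | n/N | Rate | 95% CI |
|---|---|---|---|
| IGA 0/1 | 7/27 | 25.9% | 11.1-46.3% |
| EASI-75 | 10/27 | 37.0% | 19.4-57.6% |
| EASI-50 | 14/27 | 51.9% | 31.9-71.3% |

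**3. Effect on observed EASI-75.** Let pL be the response on lebrikizumab alone, f the share of patients on topicals at the visit, and pT the chance that topicals turn a non-responder into a responder. Then observed = pL + f(1−pL)pT. All three inputs are assumed; only the top value of pT, 37%, has a source (step 2).

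| pL | f | pT | Added |
|---|---|---|---|
| 60% | 10% | 10% | 0.10 × 0.40 × 0.10 = 0.4 points |
| 50% | 25% | 20% | 0.25 × 0.50 × 0.20 = 2.5 points |
| 40% | 50% | 37% | 0.50 × 0.60 × 0.37 = 11.1 points |

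The formula treats topical use as independent of response to lebrikizumab. If use concentrates in non-responders, more of them are exposed to conversion, but their conversion rate is probably below a whole-arm rate. The two pull in opposite directions, so this is an illustration and not a bound.

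**4. Compare with sampling error.** By the normal approximation that SAP 7.10 specifies, at N = 200: 1.96 × √(0.5 × 0.5/200) = 6.9 points; at 40% or 60% it is 6.8 points.

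**5. The baseline side.** If stopping topicals raises EASI by a fraction u (assumed), returning to the on-topical level is a change of −u/(1+u): −9.1% for u = 10%, −20.0% for 25%, −33.3% for 50%, with no drug effect.

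**6. The three rescue passages side by side.** Protocol 6.3 permits topicals as needed. SAP Appendix 1 calls them rescue. Protocol 8.6.2 requires study drug to stop for rescue medication as Section 6.3 outlines it.
- If topicals do not trigger 8.6.2, the as-observed data contain topical-assisted responses.
- If they do, SAP 7.3.1 keeps only patients who completed treatment to the visit, so rescued patients largely drop out and the percentage describes those who did not need rescue.

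Either way the number needs a stated interpretation, and the interpretation differs.

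**The case against.** The strongest counter-argument is Protocol 8.6.2. Read with SAP Appendix 1, a patient who uses topicals stops study drug, and the as-observed rule then excludes later values. On that reading topical-assisted responders would largely vanish. This stands as a possible reading; the documents do not settle it. It exchanges one problem of interpretation for another.

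Several stronger readings are tempting and are not supported:
- *That topical use is unrestricted.* Protocol 6.3 ties it to flares. What is missing is a limit on potency, amount or timing.
- *That all patients restart topicals.* Inclusion criterion 6 also admits patients for whom topicals are inadvisable. The others had an inadequate topical response, which limits the likely effect.
- *That the plan has no rule for rescue anywhere.* The LOCF and MCMC-MI sections are blacked out. The SAP revision history mentions values after treatment discontinuation for them and is silent on rescue, but that does not show that a rescue rule is absent.
- *That the report would give no means of separating the two effects.* Rescue use is tabulated, concomitant medications (including steroids for asthma) are summarised by class, subgroups may be added without amendment, and IGA and EASI are also scored at screening. None of these is a pre-specified link to response, but they are not nothing.
- *That the adult study's 37.0% is a pure topical effect.* It comes from 27 adults, and the summary describes no untreated arm.

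It is also fair that efficacy is secondary and descriptive, with no inferential testing, and that SAP 7.3.1 already calls its estimand non-causal, though because of completion and not rescue.

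**Conclusion.** The point holds in a limited form. On the visible text, IGA (0,1) and EASI-75 describe lebrikizumab with as-needed topicals, measured from an off-topical baseline, and cannot be attributed to lebrikizumab alone.

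The documents give neither the amount of topical use nor response on lebrikizumab alone, so the size cannot be computed. Under the assumed ranges it runs from negligible (0.4 points) to more than the sampling error (11.1 points against about 7).

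The primary endpoint, discontinuation of study treatment due to adverse events, does not use the EASI or IGA baseline and is unaffected. A reader might infer that the efficacy results are invalid or substantially inflated; the documents do not support that. This is a matter of labelling and one missing supplementary analysis, together with a contradiction on rescue that decides which patients the as-observed tables contain.

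**What to change.** 1. **Reconcile** Protocol 6.3, Protocol 8.6.2 and SAP Appendix 1, so that it is clear whether topical use for a flare is rescue that triggers 8.6.2. Which clinical rule applies is for the sponsor; the analysis text should then follow it.
2. **Add one supplementary summary to SAP 7.10**, unless the redacted sections already contain it: IGA (0,1) with at least 2-point improvement, and EASI-75, at Weeks 4, 8, 16, 32 and 52. Count as a non-responder any patient who, since baseline, used an Appendix 1 topical or systemic AD treatment, or a systemic corticosteroid (ATC H02) for any indication, the latter taken from the concomitant medication data. Keep these patients in the denominator even if they have stopped study drug.
3. **Label the as-observed result** in SAP 7.10 as describing lebrikizumab with as-needed topicals.
4. **Report, at each of these visits, how many responders had used topicals**, as description only. Response rates compared between users and non-users would mislead, because topical use is post-baseline and related to severity.

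Permitted treatment need not change for items 2 to 4, and the treatments and their dates are already recorded in the eCRF. The cost is SAP wording and a few tables. The downside is that the summary in item 2 is conservative: one brief topical or steroid course makes a patient a non-responder through Week 52, so a lower figure will stand beside the as-observed one. Neither figure isolates lebrikizumab in a single-arm trial, but together they show how far the response depends on rescue.
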